7.5 PROHIBITED MEDICATIONS, TREATMENTS, AND PROCEDURES

Treatment with the following drugs will not be permitted unless discussed with, and approved by, the primary investigator:

- Moderate and strong CYP3A4 Inducers (should be avoided in all cases)
 - Phenytoin
 - Rifampicin
 - Enzalutamide
 - Apalutamide
 - Carbamazepine
 - Bosentan
 - Efavirenz
 - Phenobarbital
 - Primidone
 - St. John's Wort

Treatment with the following drugs is cautioned against; however, if absolutely necessary, necessitates dose reduction.

- CYP3A4 Inhibitors
 - Diltiazem
 - Erythromycin
 - Clarithromycin
 - Ketoconazole
 - Itraconazole
 - Voriconazole
 - Posaconazole
 - Fluconazole
 - Ritonavir
 - Aprepitant
 - Ciprofloxacin

- Cyclosporine
- Dronedarone
- Fluconazole
- Imatinib
- Fluovaxamine
- Verapamil

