5.4 PARTICIPANT WITHDRAWAL OR TERMINATION

5.4.1 REASONS FOR WITHDRAWAL OR TERMINATION

Patients may withdraw consent at any time for any reason or be dropped from the trial at the discretion of the investigator should any untoward effect occur that may jeopardize participant safety. In addition, a patient may be withdrawn by the investigator if enrollment into the trial is inappropriate, the trial plan is violated, or for administrative and/or other safety reasons.

A patient must be discontinued from the trial for any of the following reasons:

- The patient or legal representative (such as a parent or legal guardian) withdraws consent
- Unacceptable adverse events
- Dose delay lasting > 12 consecutive weeks
- Intercurrent illness that prevents further administration of treatment
- Investigator's decision to withdraw the patient
- The patient has a confirmed positive serum pregnancy test
- Noncompliance with trial treatment or procedure requirements
- The patient is lost to follow-up
- Administrative reasons
- Disease progression by proposed IWG response criteria for MDS/MPN¹ (Appendix H)
- Lack of response (including clinical benefit, marrow response, partial remission, complete remission) at week 24 assessment as defined by proposed IWG response criteria for MDS/MPN¹
 - a. In cases where the investigator believes a patient is clinically deriving a benefit from fedratinib despite not meeting pre-specified criteria for clinical benefit, continuation of fedratinib will need to be approved by the study PI.
- Requiring a medication/procedure on the prohibited medication/procedure list (refer to section 7.6)
- ≥ 3 dose reductions due to AE suspected to be related to study drug

The End of Treatment and Follow-up visit procedures are listed in the Schedule of Events and Section 7.3 (Visit Requirements). After the end of treatment, each patient will be followed for 30 days for adverse event monitoring. Patients who discontinue for reasons other than progressive disease will have post-treatment follow-up for disease status and toxicity up to 30 days. Follow-up rules will apply unless participant initiates a non-study cancer treatment, withdraws consent, or becomes lost to follow-up (unsuccessful attempts to contact for 3 months). After documented disease progression, each patient will be followed 104 weeks for overall survival until death, withdrawal of consent, or the end of the study, whichever occurs first.

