6.1.5 DOSING AND ADMINISTRATION

Fedratinib will be given at a dose of 400 mg PO once daily (4-100 mg capsules). Fedratinib can be given at any time during the day, but patients are advised to take the dose at the same approximate time every day. Patients are further advised to take their dose with a high fat meal as this may reduce the incidence of nausea and vomiting.

In patients taking concomitant strong CYP3A4 inhibitors that are deemed necessary by study PI (see section 7.6), fedratinib dose should be reduced to 200 mg once daily. In cases where co-administration with a strong CYP3A4 inhibitor is discontinued, fedratinib dose should be increased to 300 mg once daily during the first two weeks after discontinuation of the CYP3A4 inhibitor, and then to 400 mg once daily thereafter.

If a daily dose of fedratinib is missed, the next scheduled dose should be taken the following day. A dose will be considered “missed” if it is not administered within 8 hours of the typical time of administration. Missed doses do not need to be made up.

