6.1.6 DOSE ADJUSTMENTS/MODIFICATIONS/DELAYS

Patients will be treated at a starting dose of fedratinib 400 mg PO daily, unless they require co-administration with a strong CYP3A4 inhibitor, in which case, fedratinib dose will be reduced to 200 mg PO daily (see section 7.5). There will be no dose escalation above the 400 mg PO daily dose. Dose interruptions and modifications should occur according to the US Package Insert and protocol-defined guidelines and, when feasible, this decision should be after discussion with the study PI. Adverse events that have a clear alternative explanation or transient (≤ 72 hours) abnormal laboratory values without associated clinically significant signs or symptoms may be exempt from dose reduction rules. Hematologic AEs that precipitate dose interruptions should be monitored for recovery for at least every 7 days, if feasible.

Guidelines for Management of Gastrointestinal Adverse Events:

Gastrointestinal adverse events, specifically nausea, vomiting and diarrhea, are commonly associated with fedratinib treatment and require multifaceted management using dose adjustment, active treatment or prophylaxis with anti-emetics, and monitoring. GI symptoms generally start in the first treatment cycle but typically improve within 6-8 weeks on fedratinib treatment.

Management of Nausea and Vomiting

Management of nausea and vomiting during treatment with fedratinib will be done according to the following steps:

- Patients will be provided management instructions (including when to contact the study site) before the start of treatment.

- In order to mitigate for nausea and vomiting events, it is recommended to take fedratinib with food during an evening meal. It is highly recommended to use anti-nausea/vomiting treatment prophylactically according to local practice for the first 8 weeks of treatment (eg, ondansetron). If dimenhydrinate or other muscarinic receptor antagonists are used for nausea and vomiting, administer these agents in the evening to minimize drowsiness and other potential neurological AEs.
- Hold / reduce the dose of fedratinib
- Hospitalization may be indicated for Grade 3 or higher nausea or vomiting or events that persist
- For medications that are administered for prophylactic use of nausea and vomiting, if no clinically significant nausea and vomiting occurs during the first 8 weeks of fedratinib treatment, consider weaning the patient off these medications

Management of Diarrhea

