APPENDIX D. Moderate/strong inhibitors/inducers of CYP3A4

	Strong inhibitors	Moderate inhibitors
CYP3A4	boceprevir, cobicistat ^(h) , danoprevir and ritonavir ⁽ⁱ⁾ , elvitegravir and ritonavir ⁽ⁱ⁾ , grapefruit juice ^(k) , indinavir and ritonavir ^(j) , itraconazole ^(h) , ketoconazole, lopinavir and ritonavir ^(h,j) , paritaprevir and ritonavir and (ombitasvir and/or dasabuvir) ⁽ⁱ⁾ , posaconazole, ritonavir ^(h,j) , saquinavir and ritonavir ^(h,j) , telaprevir ^(h) , tipranavir and ritonavir ^(h,j) , telithromycin, troleandomycin, voriconazole	aprepitant, ciprofloxacin, conivaptan ^(l) , crizotinib, cyclosporine, diltiazem ^(m) , dronedarone ^(h) , erythromycin, fluconazole ^(f) , fluvoxamine ^(a) , imatinib, tofisopam, verapamil ^(h)

	Strong inducers	Moderate inducers
CYP3A	apalutamide, carbamazepine ^(e) , enzalutamide ^(g) , mitotane, phenytoin ^(b) , rifampin ^(a) , St. John's wort ^(h)	bosentan, efavirenz ^(f) , etravirine, phenobarbital, primidone

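### For the ten listed CYP3A4 inhibitors that Appendix D classes as moderate, section 7.5 requires a lower fedratinib dose while section 6.1.6 keeps the 400 mg starting dose

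*Combined protocol and SAP*

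**What the plan says.** Five parts of the protocol bear on a patient who needs a CYP3A4 inhibitor, and one eligibility criterion touches the same question.

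- Section 7.5 stands under the heading "PROHIBITED MEDICATIONS, TREATMENTS, AND PROCEDURES" and has two tiers. Inducers need the investigator's approval and are to be avoided. For inhibitors the rule is: "Treatment with the following drugs is cautioned against; however, if absolutely necessary, necessitates dose reduction". One undivided list follows, with no dose.
- Section 6.1.5 addresses strong inhibitors: for "concomitant strong CYP3A4 inhibitors that are deemed necessary by study PI (see section 7.6), fedratinib dose should be reduced to 200 mg once daily". It does not mention moderate inhibitors. Its step back up to 400 mg after the inhibitor stops is also written for strong inhibitors only.
- Section 6.1.6 sets the general rule: "Patients will be treated at a starting dose of fedratinib 400 mg PO daily, unless they require co-administration with a strong CYP3A4 inhibitor". In that case the dose is 200 mg. The sentence refers the reader to 7.5.
- Appendix D sorts inhibitors into strong and moderate columns. The moderate column begins "aprepitant, ciprofloxacin".
- Section 5.4.1 lists the following among the reasons for which a patient must be discontinued: "Requiring a medication/procedure on the prohibited medication/procedure list (refer to section 7.6"). Section 7.6 deals with prophylactic anti-emetics.
- Exclusion criterion 9 (section 5.2) bars, at entry, moderate or strong CYP3A4 inducers and drugs that inhibit both CYP3A4 and CYP2C19. For classification it sends sites to an external FDA table.

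**The concern.** A dosing instruction should give one answer for one co-medication. Here the answer for a moderate inhibitor depends on which section a site opens: 7.5 calls for a reduction, and 6.1.6 leaves the starting dose unchanged. A site that follows 7.5 is also given no dose to reduce to.

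The two references to 7.6 add to the difficulty, because they cite the same unrelated section for opposite actions: take the patient off the trial, or continue at a lower dose.

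At stake is consistent exposure across the four sites in a 25-patient single-arm trial, and with it the reading of the safety and response data.

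**Working it through.** No sample-size or power figure is involved. The check is a count and a side-by-side reading.

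**Step 1: count the list in 7.5.** There are 17 entries. Fluconazole appears twice, so 17 − 1 = 16 distinct drugs. (One name is misspelled and is taken to be fluvoxamine.)

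**Step 2: match each drug to Appendix D.**

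| Class in Appendix D | Drugs listed in 7.5 | Count |
|---|---|---|
| Moderate | diltiazem, erythromycin, fluconazole, aprepitant, ciprofloxacin, cyclosporine, dronedarone, imatinib, fluvoxamine, verapamil | 10 |
| Strong | ketoconazole, itraconazole, voriconazole, posaconazole, ritonavir | 5 |
| Neither column | clarithromycin | 1 |

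10 + 5 + 1 = 16, and 10/16 = 62.5% of the listed names.

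**Step 3: apply each section to each class.**

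| Class | 7.5 | 6.1.5 | 6.1.6 | Do these agree? |
|---|---|---|---|---|
| Moderate (10) | reduce, dose not stated | silent | start at 400 mg | No |
| Strong (5) | reduce, dose not stated | 200 mg | 200 mg | Yes, on reduction |
| Clarithromycin (1) | reduce, dose not stated | depends on class | depends on class | Cannot be told from Appendix D |

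The direct conflict is between 7.5 and 6.1.6, for the ten moderate drugs, at the starting dose. It comes from the exception clause in 6.1.6, which lifts the 400 mg rule for strong inhibitors alone. If a moderate inhibitor is added during treatment, 7.5 still calls for a reduction, and neither 6.1.5 nor 6.1.6 supplies a dose for it.

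**Step 4: follow the cross-references.** Section 6.1.6 cites 7.5, where the inhibitor list is. Sections 5.4.1 and 6.1.5 cite 7.6, where there is neither a prohibited list nor a rule on inhibitors. Both references to 7.6 are therefore wrong.

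**Step 5: test whether 5.4.1 reaches the inhibitors.** They stand under the heading of 7.5 that speaks of prohibition, which points to yes. The text of 7.5 then discourages them but allows them on a condition, which points to no. Because the reference in 5.4.1 is wrong, it cannot settle the matter.

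**The case against.** The strongest reply is that the conflict is narrow and partly managed.

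- **The sections agree for strong inhibitors, and 6.1.5 does not limit reduction to them.** Both points stand. The contradiction is confined to the moderate drugs and rests on 6.1.6.
- **6.1.6 refers to 7.5, so the two were meant to be read together.** That shows the intention, but a reader who follows the reference finds a list made up mostly of moderate drugs under a broader rule, and so meets the conflict.
- **There is central oversight.** Section 6.1.6 asks for discussion of dose changes with the study PI when feasible, 6.1.5 leaves the need for a strong inhibitor to the study PI, and section 7.1.4 has the study PI review eligibility for collaborating sites. This may reduce divergence between sites, but it does not say which text governs. Section 6.1.6 also defers to the US Package Insert, but alongside the protocol's own guidelines, and it is those that disagree.
- **Exclusion criterion 9 may keep some of these drugs out at entry.** This is possible. The documents do not say which listed drugs inhibit both enzymes, so it is not shown that all ten could be in use when treatment starts. The criterion also relies on an external table, so clarithromycin's absence from Appendix D means only that the appendix does not classify it.

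A reader might go further and infer that 5.4.1 requires discontinuation, so that one co-medication leads to full dose, reduced dose or no drug. The documents do not establish this. It depends on treating a conditionally allowed drug as prohibited on the strength of a section heading, and 5.4.1 can equally be read as reaching the inducers only.

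A reader might also infer that the conflict is bound to arise often. The documents give no frequency of inhibitor use, and the anti-emetics that they name as examples (ondansetron, dimenhydrinate) are not on the list in 7.5.

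**Conclusion.** The point holds in a limited form, and the text is wrong as written. For 10 of the 16 distinct inhibitors in 7.5, following 7.5 and following 6.1.6 give different starting doses: an unstated dose below 400 mg under one, 400 mg under the other. For 5 there is no disagreement on reduction among 6.1.5, 6.1.6 and 7.5. For 1, clarithromycin, Appendix D does not show whether the strong-inhibitor rule applies. Two cross-references to 7.6 are wrong, and the reach of 5.4.1 is ambiguous.

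This rests on taking Appendix D as the protocol's classification and on reading the exception in 6.1.6 literally. The 62.5% describes drug names, not patients or exposure.

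It would be tempting to conclude that the primary endpoint is biased. Section 10.4.2 does count a patient who does not complete three cycles as a non-responder, so doses received and discontinuations could feed into response. But nothing in the documents allows the size or direction of such an effect to be estimated, and the stated design (25 patients, 80% power, one-sided 0.05) is not touched.

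**What to change.** Reconcile exclusion criterion 9 in section 5.2, sections 5.4.1, 6.1.5, 6.1.6 and 7.5, and Appendix D, in one amendment:

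1. Give each inhibitor listed in 7.5 one stated action, worded the same way in 6.1.5, 6.1.6 and 7.5. If that action is a reduction, state the dose.
2. State whether the discontinuation rule in 5.4.1 covers the inhibitors or only the inducers.
3. Make clarithromycin's status consistent between 7.5 and Appendix D, and remove the duplicate fluconazole entry.
4. State whether Appendix D or the external table cited in exclusion criterion 9 governs classification.
5. Correct the references to 7.6 in 5.4.1 and 6.1.5.

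Which rule and which dose apply is for the sponsor to decide. The cost is amendment wording and notice to the sites. The sample size, endpoints and analyses do not change.

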7.6 PROPHYLACTIC MEDICATIONS, TREATMENTS, AND PROCEDURES

Prophylactic anti-emetics (e.g. ondansetron) are highly recommended during the first 8 weeks of treatment with fedratinib. See section 6.1.6 for detailed guidance.

7.7 RESCUE MEDICATIONS, TREATMENTS, AND PROCEDURES

- In the setting of leukocytosis $> 50,000/\mu\text{L}$, hydroxyurea can be provided up to a dose of 2,000 mg per day per the discretion of the treating physician. For hydroxyurea use outside of these parameters, use will be determined after discussion with the PI.
- In the setting of anemia ($\text{Hgb} < 11 \text{ g/dL}$) and EPO level < 500 , erythropoiesis-stimulating agent (ESA) can be provided at the discretion of the treating physician. Patients who start ESA within 2 months of study enrollment or while on study will not be eligible for anemia response.
- Growth factor support with granulocyte stimulating factor may be administered for patients with an absolute neutrophil count (ANC) $< 500/\mu\text{L}$ per the discretion of the treating physician.
- The use of transfusion support (RBCs and platelets) will be according to standard of care as rescue therapy for anemia or thrombocytopenia.
- Corticosteroids and antihistamines may be administered per institutional protocol for the treatment of hypersensitivity reactions should they emerge.
- Loperamide should be available at home for each patient enrolled on the study. Treatment with loperamide should be directed by the treating physician based on local practices. Consider starting loperamide at a 4 mg loading dose at the onset of diarrhea and giving 2 mg after each diarrheal bowel movement without exceeding 16 mg/24 hours.
- See section 6.1.6 for detailed guidance on management of expected toxicities.

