2 INTRODUCTION: BACKGROUND INFORMATION AND SCIENTIFIC RATIONALE

2.1 BACKGROUND INFORMATION

Disease Background

Myelodysplastic/Myeloproliferative Neoplasms (MDS/MPNs) and chronic neutrophilic leukemia (CNL) are heterogeneous myeloid malignancies that are characterized by proliferative features, bone marrow dysfunction, complex molecular features, and poor outcomes.² Clinically and genetically, these diseases have significant overlap and are better viewed as a continuum of disease rather than distinct disease entities.² Treatment is typically symptom-directed and based on extrapolation from other, related disease entities. Therapeutic options have traditionally included cytoreductive agents such as hydroxyurea and hypomethylating agents such as azacitidine and decitabine.³⁻⁶ With the exception of azacitidine and decitabine for CMML, there are currently no FDA-approved therapies for these indications. Allogeneic hematopoietic cell transplant (AHCT) offers a curative option for some patients, but the majority of patients are not eligible for this procedure due to age, comorbidities, or lack of a suitable donor.⁷⁻¹³ Clinical trials represent a preferred option, but these diagnoses are often excluded from clinical trials that specifically enroll myelodysplastic syndrome (MDS) or MPN patients.¹⁴

Upregulation of the Janus kinase (JAK)/Signal transducer and activator of transcription (STAT) pathway is a hallmark of MPNs. This results in cell proliferation, inhibition of cell death and clonal expansion of myeloproliferative malignant cells.¹⁵ JAK2 inhibitors that downregulate the JAK/STAT pathway can be expected to reduce cell proliferation and induce malignant cell killing in MPN patients. To that end, JAK2 inhibitors have been shown to improve disease-related symptoms and splenomegaly in patients with MF.¹⁶⁻¹⁹

Preclinical work has shown that MDS/MPNs feature GM-CSF hypersensitivity that can be abrogated with JAK

inhibition.²⁰ Additionally, driver mutations involving the JAK/STAT pathway are frequently present in MDS/MPNs and CNL.² Several small studies assessing JAK inhibition in MDS/MPNs with ruxolitinib have shown activity in this setting.²¹⁻²³

Study Agent Background

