10.4 DESCRIPTION OF STATISTICAL METHODS

10.4.1 GENERAL APPROACH

This will be a phase 2 trial to assess the efficacy of fedratinib in MDS/MPN and CNL. Patients with a

diagnosis of MDS/MPN-U, aCML, MDS-MPN-RS-T, or CNL will be enrolled using modified Simon's minimax 2-stage approach.³¹ The primary endpoint of the study is the proportion of patients achieving an objective clinical response at week 24 which is determined based upon the Modified MDS/MPN IWG Proposed Response Criteria.

An interim analysis will be performed after 9 patients have completed their week 24 disease assessment or have discontinued study treatment prior to week 24 to assess for futility. If there are ≥ 3 responses among these 9 patients, an additional 16 patients will be enrolled for a total of 25. This will be sufficient to test our hypothesis that fedratinib will increase the ORR from a historical standard of 30% to 55% using a power of 80% and a one-sided type 1 error rate of 0.05. The null hypothesis will be rejected if 12 or more responses are observed.

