10.4.2 ANALYSIS OF THE PRIMARY EFFICACY ENDPOINT(S)

The primary endpoint is overall response rate. This is defined as the proportion of patients achieving a clinical response from baseline to week 24. Clinical response is defined as those achieving complete response, partial response or clinical benefit per Modified MDS/MPN IWG Proposed Response Criteria. Formal response assessments will be performed after cycle 3, cycle 6 and every 6 cycles thereafter. If a patient does not complete 3 cycles (does not undergo formal response assessment), the patient will be considered a non-responder. A patient who completes at least 3, but not 6 cycles, will have week 24 response assessment carried forward from week 12.

Patients lacking evidence of response, whether this is due to failure to meet response criteria or unavailable information to determine response, will be considered non-responders.

The p-value and confidence interval will be computed by using conditional distribution in order to reflect the nature of two-stage design.³²

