10.4.7 PLANNED INTERIM ANALYSES

The interim efficacy review will take place after 9 patients are evaluable for efficacy (i.e., completed week 24 disease assessment or discontinued study treatment prior to week 24). Enrollment will be halted if there are ≤ 2 responses among the first 9 patients. Enrollment will not be stopped while waiting for the first 9 patients to become evaluable for efficacy. If ≥ 3 responses are seen in the first 9 patients, an additional 16 patients will be enrolled for a total enrollment of 25 patients.

Overall response data will be presented in aggregate.

Individual patient TSS, PGIC will be measured at week 12 and week 24 assessment and presented as a function of time.

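### A spleen, symptom or white-count benefit reached on new or increased hydroxyurea, or a hemoglobin rise under red-cell transfusion, can count as a primary response because no scoring rule excludes it

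*Combined protocol and SAP*

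**What the plan says.** - **Rescue.** Section 7.7 states that, when leukocytosis exceeds 50,000/µL, "hydroxyurea can be provided up to a dose of 2,000 mg per day per the discretion of the treating physician". Use outside those limits follows discussion with the PI. On transfusion it states: "The use of transfusion support (RBCs and platelets) will be according to standard of care as rescue therapy for anemia or thrombocytopenia". The only scoring consequence attached to any rescue agent in 7.7 is for ESA: "Patients who start ESA within 2 months of study enrollment or while on study will not be eligible for anemia response".
- **Endpoint.** Section 10.4.2: "Clinical response is defined as those achieving complete response, partial response or clinical benefit per Modified MDS/MPN IWG Proposed Response Criteria". Under Appendix F, clinical benefit needs only one of an erythroid, platelet, neutrophil, spleen or symptom response, without progression. An Appendix F footnote adds that resolution of abnormal counts, including leukocytosis, may itself be clinical benefit.
- **Non-response.** Sections 10.3 and 10.4.2 assign it for early discontinuation, unmet criteria or missing information. Neither mentions rescue.
- **Hydroxyurea as an active drug.** Section 2.1 notes that "Therapeutic options have traditionally included cytoreductive agents such as hydroxyurea". Section 7.1.15 requires new baseline spleen imaging if hydroxyurea was started, stopped or changed since the last scan. Exclusion criterion 10 in 5.2 requires a stable dose for more than 14 days before fedratinib.

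**The concern.** The plan controls hydroxyurea changes up to the first dose and then stops controlling them. A patient whose white count exceeds 50,000 may start or increase hydroxyurea, and at week 24 show a smaller spleen, a lower symptom score or a normal white count. As written, that patient can be scored as a responder, although the plan accepts elsewhere that hydroxyurea can change spleen size. The ESA rule shows that the authors recognized this kind of confounding and dealt with it for one agent.

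There is no concurrent control in which rescue would act equally. Every rescue-assisted response adds directly to the count used for the 3-of-9 interim decision and the 12-of-25 final test. With no written rule, whether a rescued patient counts would be settled case by case, in an open-label trial, by people who know the running total.

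**Working it through.** **1. Can the route be completed under the text?**

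- *Hydroxyurea.* It is not on the section 7.5 lists, and starting it is not a reason for withdrawal in 5.4.1. The spleen and symptom components of Appendix F carry no hydroxyurea condition, and neither does the footnote on count resolution. The requirement of no progression does not block the route, because leukocytosis is not a progression criterion in Appendix H. The verification at 8 weeks or more (the line is garbled in the text) does not block it if hydroxyurea continues.
- *Red-cell transfusion.* CR hemoglobin must be held without transfusion, and the alternative erythroid route requires transfusion independence for at least 8 weeks. The line for a hemoglobin rise of at least 2.0 g/dL has no such condition.

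**2. The plan's own figures**

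Inputs from 10.4.1 and 10.4.7: null 30%, alternative 55% ("fedratinib will increase the ORR from a historical standard of 30% to 55" per cent), "using a power of 80% and a one-sided type 1 error rate of 0.05". Stage 1 has 9 patients and continues at 3 or more responses; then "an additional 16 patients will be enrolled for a total enrollment of 25 patients". The null is rejected at 12 or more.

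P(reject | p) = Σ over x = 3,…,9 of C(9,x) pˣ(1−p)⁹⁻ˣ × P[Bin(16,p) ≥ 12−x]

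- p = 0.30: 0.0421, within the 0.05 limit
- p = 0.55: 0.8007, matching the stated 80%

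The design arithmetic is correct. The issue is what is counted as a response.

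**3. Effect of rescue-made responses on type I error**

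Let c be the share of true non-responders turned into scored responders by rescue. The documents give no value, so c is assumed. Scored null rate = 0.30 + 0.70c; expected extra responders in 25 = 25 × 0.70c.

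| c (assumed) | Scored rate | Extra responders in 25 | P(reject) |
|---|---|---|---|
| 0 | 0.300 | 0 | 0.042 |
| 1.4% | 0.310 | 0.25 | 0.053 |
| 5% | 0.335 | 0.875 | 0.09 |
| 10% | 0.370 | 1.75 | 0.17 |

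The second row solves 0.30 + 0.70c = 0.31, so c = 0.01/0.70 = 0.014. A value of c = 5% would arise, for example, if 10% of patients were rescued and rescue made a response in half of those who would otherwise not respond. The chance of passing the interim at a true 30% also rises, from 0.537 to 0.564 at a scored 31% and 0.708 at 37%.

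**4. Power cost of the strictest possible rule**

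Suppose every rescued patient is scored a non-responder, with rescue independent of response. The scored rate under the alternative is then 0.55(1−f), where f is the assumed share rescued.

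- f = 0: power 0.801
- f = 5%: 0.55 × 0.95 = 0.5225, power 0.717
- f = 10%: 0.55 × 0.90 = 0.495, power 0.618

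A component-level rule voids fewer responses than this, so under the same assumption these figures bound its loss.

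**The case against.** Several stronger readings are tempting, and the documents do not support them.

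- *ESA is the only agent that ever disqualifies a response.* This holds within 7.7 only. Appendix F requires CR hemoglobin and platelets to be held without transfusion, tests transfused patients by transfusion independence, and excludes cytokine treatment when judging the fall in precursors and monocytes.
- *Hydroxyurea alone could produce CR or PR.* This is implausible. CR needs marrow, fibrosis, hemoglobin, platelet and extramedullary criteria together. PR needs normalized counts and resolved hepatosplenomegaly, with a blast reduction unless baseline blasts are 5% or less. The realistic exposure is clinical benefit. Its symptom route is narrower still, because Appendix F does not treat scores below 20 as eligible.
- *Transfusion readily creates responses.* For red cells the gap is one line. A single transfusion would be unlikely to hold a 2 g/dL rise through an 8-week verification, though repeated transfusion could. Transfusion dependence is a progression criterion, but a minor one that is not sufficient alone.
- *Rescued patients are those failing fedratinib.* This is not established. Dose interruption for toxicity, or a high white count at entry, could also lead to hydroxyurea.

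Two further objections deserve an answer. Section 10.4.3 requires palpation responses to agree with imaging, but it does so under the secondary spleen endpoint, and imaging confirms shrinkage, not its cause. The other objection stands: the documents do not say whether the 30% standard came from patients who could receive hydroxyurea. If it did, the inflation shown is too large and a strict exclusion would weaken comparability.

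**Conclusion.** The concern holds in limited form and should be fixed. A spleen, symptom or white-count clinical benefit reached on new or increased hydroxyurea, and a hemoglobin rise supported by transfusion, can be scored as fedratinib responses, because nothing in 7.7, 10.3, 10.4.2 or Appendix F says otherwise.

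A reader might infer that the trial's error rate is in fact 0.09 or 0.17. The documents do not support that: those figures rest on assumed conversion of 5% and 10%, and on a 30% standard free of hydroxyurea-assisted responses. What does not depend on a guess about rescue frequency is how little room there is. The exact type I error is 0.042, and a rise of one percentage point in the scored null rate takes it past 0.05.

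**What to change.** Leave the rescue provisions of 7.7 unchanged. In 10.4.2, before the 9-patient interim, extend the existing ESA-type scoring rule at component level:

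1. A spleen, symptom or WBC/platelet-count clinical benefit is not counted if the patient was receiving hydroxyurea that was newly started, or above the stable entry dose, within a pre-specified window before the assessment. The 8-week verification period is one option. A short course that ended before the window does not void the response.
2. The hemoglobin-rise criterion counts only if no red-cell transfusion was given in the 8 weeks before the assessment.
3. A patient with no other qualifying component is a non-responder. The same rule applies to a week 12 assessment that is carried forward.
4. The response count ignoring rescue is reported as a sensitivity analysis.

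It would also help to state whether the 30% standard allowed hydroxyurea.

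The cost is a few sentences, plus capture of hydroxyurea dose changes and transfusion dates; 7.1.8 already records medications. The ORR may be somewhat lower and some power is lost, bounded as in step 4 of the working. The operating characteristics of the chosen rule should therefore be reported over a range of rescue frequencies.
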